### **PRN treatment period: Day 61 to Day 180**

Efficacy and safety assessments will be repeated (see Table 6-1) at Day 90, 120, 150 and 180. All subjects will attend Scheduled Study Visits every 30 ( $\pm 7$ ) days. The primary endpoint will be evaluated when patients have completed assessments at the Day 90 visit.

Between the Day 90 and Day 150 visits inclusive, the decision to administer ranibizumab 0.5mg will be at the discretion of the Investigator and driven either by persistent or worsening visual symptoms attributed by the Investigator to nAMD, or worsening visual acuity ( $>1$  letter decline since last Study Visit) or by the presence of persistent or worsening disease activity on OCT\*. Source documentation must provide evidence for one or more of these retreatment criteria. Injections of IVT ranibizumab to the study eye, where required, should occur on the same day as the scheduled study visit.

Final efficacy and safety assessments will be conducted at Day 180.

---

\* Persistent or worsening disease activity on OCT includes the presence of sub-retinal fluid, persistent or increased number, size or total volume of IRCs, or increased central retinal or foveal thickness, or similar quantitative retinal imaging data recorded within the individual patient record.

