#### **5.5.4.2 PRN Treatment Period: Day 90 to Day 180**

All patients will have monthly assessments of BCVA and disease activity assessed by OCT. These assessments, together with an assessment of the patient's visual symptoms, will be used for the decision of potential re-treatment with ranibizumab. This PRN regimen, will permit re-treatment with ranibizumab at Day 90, Day 120 and/or Day 150 if in the opinion of the Investigator persistent or worsening visual symptoms are attributed to nAMD, and/or if there is evidence of worsening ETDRS best corrected visual acuity (>1 letter decline since last Study Visit) and/or the presence of persistent or worsening disease activity on OCT\*. Source documentation must provide evidence for one or more of these retreatment criteria.

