\* Persistent or worsening disease activity on OCT includes the presence of sub-retinal fluid, persistent or increased number, size or total volume of IRC, or increased central retinal or foveal thickness, or similar quantitative retinal imaging data recorded within the individual patient record.

Treatment for non-nAMD indications with anti-angiogenic drugs including ranibizumab in the fellow eye is prohibited.

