## **6.3 Treatment exposure and compliance**

### **Treatment exposure**

Treatment exposure to ranibizumab will be assessed for both study eye and fellow treated eye as well as total exposure (study eye and fellow eye). Information regarding study treatment administration (ranibizumab) in the study eye will be collected on the drug administration record eCRF. Treatment of the fellow eye with ranibizumab will be captured on a separate eCRF.

The reason for dosing of ranibizumab or the reason for dose/no dose will be described on the drug administration record eCRF for the study eye.

At every visit, it needs to be reported within the eCRF if treatment or no treatment with study drug has been administered to the patient both for the study eye and the fellow eye.

In addition, confirmation of disease activity as assessed by the Investigator through functional and anatomical parameters detected by BCVA and OCT will be captured for the study eye (please see Section 5.5.4.2).

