## **Compliance to treatment regimen**

The evaluation of compliance will assess whether ranibizumab injections were administered according to the protocol specified regimen during the monthly treatment period and according to the Investigator's assessment of disease activity during the PRN treatment period.

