### **6.4.1 Optical Coherence Tomography**

Optical Coherence Tomography (OCT) images are to be taken using High Definition (HD)/Spectral Domain (SD) optical coherence tomography (OCT) equipment. Patients must be assessed using the same machine throughout the course of the study.

The Investigator will perform OCT at visits indicated in Table 6-1 according to a standardized imaging protocol as specified in the Procedure Manual. The information collected will be used by the Investigator to assess the status of disease activity; i.e., decisions on subject eligibility as well as decisions on PRN treatment are based on his/her own evaluation.

The Investigator will send the digital raw images taken monthly from Screening to Day 180 to the Central Reading Center (CRC) as soon as possible after the Scheduled Study Visit; the images will be transferred electronically using the dedicated SD/HD-OCT software format. No transmission of imaging data on print-outs will be accepted. The captured images will contain quantitative parameters (i.e., the Subfoveal Retinal Thickness (SRT), the Central Subfield Retinal Thickness (CSRT), Central Subfield Retinal Volume (CSRV), PED height, SRF volume, IRC volume, and the subfoveal choroidal thickness), as well as the presence or absence of qualitative parameters (IRC, intraretinal fluid, SRF, hemorrhage, dry retina, or other). The CRC will evaluate the images and the results of the CRC assessments will be transferred to the CRO responsible for data management.

The CSRT represents the average retinal thickness ( $\mu\text{m}$ ) of the circular area within 1 mm diameter around the foveal center. The CSRV represent the total retinal volume ( $\mu\text{m}^3$ ) of the circular area within 1mm around the foveal center. Both CSRT and CSRV are based on the automatically determined values from the dedicated SD/HD-OCT software. Before accepting the values provided by the dedicated SD/HD-OCT software, the OCT image acquisition technician must ensure adequate image quality for the assessment of the CSRT. Specifically the technician must exclude any artifacts of the automated segmentation. If artifacts are identified, a manual correction of segmentation lines must be done.

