2.1.7 Treatment exposure

Treatment exposure to ranibizumab will be summarized by subgroup and overall for the SAF, and will include:

- Duration of exposure to ranibizumab for both study eye and fellow treated eye, as well as total duration of exposure (study eye and fellow eye). Duration of exposure will be calculated as date of last ranibizumab injection – date of first ranibizumab injection + 1, for study eye, fellow treated eye and both eyes together
- Total number of injections overall the study course and number of injections by visit (including unscheduled visits), for both study eye and fellow treated eye
- Number and percentage of patients who received bilateral injections of ranibizumab (both the study eye and fellow eye injected at the same visit) by visit
- Reason for PRN treatment (BCVA decline, or OCT criteria) by visit during the PRN treatment period, for study eye
- Reason for no dosing by visit, for study eye. Prior to database lock, a complete list of reasons for no dosing during the Monthly treatment period, as recorded on the eCRF, will be provided by ██████ to Novartis in an Excel spreadsheet. Novartis will review them and classify them as ocular or non-ocular.
- Compliance to treatment regimen, for study eye

Compliance to treatment regimen will be assessed as follows

- Monthly treatment period, compliance= $100 * (\text{number of injections in study eye} / 3)$
- PRN treatment period, compliance= $100 * (\text{number of injections done in study eye} / \text{number of required injections in study eye based on changes in patient symptoms, BCVA or OCT})$

An injection will be considered as required if:

- in the opinion of the Investigator persistent or worsening visual symptoms are attributed to nAMD and/or
- there is evidence of worsening early treatment diabetic retinopathy study (ETDRS) BCVA (>1 letter decline since last Study Visit) and/or
- the presence of persistent or worsening disease activity on OCT (presence of sub-retinal fluid, persistent or increased number, size or total volume of IRC, or increased central retinal or foveal thickness)

All treatment exposure to ranibizumab details, including derived variables, will be listed.

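### SAP 2.1.7 computes PRN compliance as all injections done over injections required, without matching by visit, so an untriggered injection can conceal a missed one

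*SAP*

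**What the plan says.** SAP 2.1.7 (Treatment exposure) includes compliance for the study eye among the Safety Set exposure summaries. For the PRN period the numerator is the "number of injections done in study eye" and the denominator is the number of injections required. The visible text does not limit the numerator to visits where an injection was required, and it gives no rule for a patient with none required.

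An injection is required if any of three criteria is met: symptoms that the Investigator attributes to nAMD, a fall of more than one letter since the last visit, or persisting or worsening OCT activity. The SAP follows the OCT criterion with a bracket: "presence of sub-retinal fluid, persistent or increased number, size or total volume of IRC, or increased central retinal or foveal thickness".

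The protocol's footnote to section 3.1 words the OCT criterion openly: "Persistent or worsening disease activity on OCT includes the presence of sub-retinal fluid, persistent or increased number, size or total volume of IRCs". The same list in the footnote to 5.5.4.2 ends with "or similar quantitative retinal imaging data recorded within the individual patient record". Section 5.5.4.2 sets the treatment visits: the regimen "will permit re-treatment with ranibizumab at Day 90, Day 120 and/or Day 150".

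Protocol 6.3 frames PRN compliance differently. It asks whether injections followed the Investigator's "assessment of disease activity during the PRN treatment period", and says of the study eye that "confirmation of disease activity as assessed by the Investigator through functional and anatomical parameters detected by BCVA and OCT will be captured".

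**The concern.** Compliance in a PRN period should answer one question: when an injection was indicated, was it given? A ratio of two unlinked totals does not answer it. An injection given without a trigger adds to the numerator and nothing to the denominator, so it can cancel a missed one or take the percentage past 100. A patient whose disease is quiet throughout, an ordinary outcome of PRN dosing, has a zero denominator.

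At stake is one reported percentage. A reader of the study report could take 100% to mean that every indicated injection was given when one was not. There is also a smaller alignment point. If the SAP bracket were programmed as a closed list, an injection given solely on the protocol's residual imaging category would count as done but not as required.

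**Working it through.** **Inputs.** The formula is from SAP 2.1.7. There are three PRN treatment visits, Day 90, 120 and 150, from Protocol 5.5.4.2. The plan gives no compliance figure to reproduce and no frequencies, so the patient patterns below are hypothetical.

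**Formulas.** At visit v, let R = 1 if an injection was required and G = 1 if one was given.

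- SAP ratio = 100 × ΣG / ΣR
- Visit-matched ratio = 100 × Σ(R×G) / ΣR
- Difference = 100 × Σ((1−R)×G) / ΣR, that is, untriggered injections over required injections

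The two agree exactly when there are no untriggered injections.

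| Required | Given | SAP ratio | Visit-matched |
|---|---|---|---|
| Day 90, 120 | Day 120, 150 | 2/2 = 100% | 1/2 = 50% |
| Day 90 | Day 90, 120 | 2/1 = 200% | 1/1 = 100% |
| Day 90 | Day 120, 150 | 2/1 = 200% | 0/1 = 0% |
| None | Any | undefined | undefined (needs a rule) |

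**All patterns.** Three visits give 2³ × 2³ = 64 required-by-given patterns. These counts show what the formula allows; they are not probabilities.

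- Undefined (none required): 1 × 8 = 8.
- SAP ratio differs from matched: one required, 3 × 6 = 18; two required, 3 × 4 = 12; total 30.
- SAP ratio above 100%: one required and at least two given, 3 × 4 = 12; two required and three given, 3 × 1 = 3; total 15. The matched ratio never exceeds 100%.
- SAP ratio at least 100% although a required injection was missed: one required, 3 × 3 = 9; two required, 3 × 2 = 6; total 15.

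**OCT wording, if the bracket were read as closed.** Suppose all three injections were indicated and given, one of them only on the residual category: 3/2 = 150% instead of 3/3 = 100%. Suppose three were indicated and two given, the missed one resting only on the residual category: 2/2 = 100% instead of 2/3 = 66.7%. If an assumed share f of patients resembled the first case and all others scored 100%, the group mean would be 100(1−f) + 150f: 100.5% at f = 1%, 102.5% at 5% and 105% at 10%. The documents give no value for f.

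**Does aligning the wording suffice?** Give each visit one of three trigger states (listed, residual only, none) and an injection given or not: 6³ = 216 patterns. The ratio exceeds 100% in:

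- 54 with the closed list: 3 × 4 × 4 = 48 with one listed trigger, plus 3 × 2 × 1 = 6 with two.
- 36 with the protocol wording and the numerator unchanged: 3 × 2 × 4 = 24 with one required, plus 3 × 4 × 1 = 12 with two.
- 0 with the visit-matched numerator.

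The numerator is therefore the main defect.

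**The case against.** Injections done over injections required is a simple dose count, and the monthly formula beside it (injections over 3) is built the same way. A value above 100% can be read as over-treatment. With the protocol's OCT wording in place, it needs an untriggered injection, which already departs from the rule that source documents evidence a re-treatment criterion; SAP 2.1.3 lists all deviations. SAP 2.1.7 also shows injections by visit, reasons for PRN treatment, reasons for no dosing, and patient listings.

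Much of this stands as a limit on harm. A careful reader could reconstruct what happened from the listings. But those outputs do not correct the percentage, and a value of exactly 100% gives no signal to look further. The comparison with the monthly period is weak: every visit there requires an injection, so with injections given only at those visits the count and the match coincide.

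A reader might infer something stronger: that the SAP holds sites to a narrower OCT rule than the protocol's. The documents do not support that. The SAP bullet keeps the protocol's general criterion and adds the bracket after it, plausibly as a shortened gloss. The SAP's own list of changes says the reading center has no robust way to assess IRC volume, which the bracket names, so the bracket would work poorly as a closed rule on centrally graded data. Protocol 6.4.1 says "decisions on subject eligibility as well as decisions on PRN treatment are based on his/her own evaluation", and 6.3 cross-refers to 5.5.4.2, whose footnote contains the residual category. If the Investigator's record is the source, the mismatch does not arise.

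**Conclusion.** The concern holds for the numerator. As written, the PRN ratio can report 100% with a required injection missed, can exceed 100%, and is undefined when none was required. The error for any patient equals untriggered injections divided by required injections. How many patients that touches cannot be estimated from the documents and may be small.

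The OCT wording is a secondary point, conditional on the bracket being programmed literally.

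A reader might also infer that efficacy conclusions are at risk. They are not. The ratio is one descriptive Safety Set summary. Injection counts and reasons for treatment are reported independently of it. The Day 90 CSRT change does not use it, and Protocol 6.4 places efficacy assessments before any injection at the same visit. Per-protocol exclusions run through deviation codes (SAP 2.1.3); the deviation list itself is not visible, so nothing is assumed about it.

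This is a minor correction. It rests on the visible SAP text containing the whole rule and on three PRN treatment visits.

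**What to change.** Amend SAP 2.1.7 as follows.

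1. At each of Day 90, 120 and 150, count in the numerator only an injection given for a visit where one was required. Attribute a delayed injection (Protocol 5.5.4) to the scheduled visit that triggered it.
2. Show untriggered injections as a separate count.
3. Report patients with no required injection as not applicable, with their number.
4. As a secondary alignment, replace the bracket with the protocol's full OCT wording, including its open-ended verb and the residual imaging category, so that it is not programmed as a closed list.

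The SAP should also name the data source for a required injection. The Investigator's captured assessment fits Protocol 6.3. Because re-treatment is discretionary, however, relying on that judgement alone could pull compliance toward 100%, so the choice should be deliberate.

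The cost is a few lines of SAP text and one visit-level derivation. The existing denominator already needs the required status at each visit, so the matched numerator adds only the link from a delayed injection to its visit. No protocol change is needed.

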2.2 Efficacy evaluation

2.2.1 Primary objective

The primary objective is to demonstrate that the mean change from baseline in CSRT as determined by OCT at Day 90 is less than zero.

2.2.1.1 Variables

The primary variable will be the difference from baseline to Day 90 in CSRT.

[figure not shown]
2.2.1.2 Descriptive analyses

The change in CSRT from baseline to Day 90 will be summarized together with the 95% CI for the mean and absolute values of CSRT at baseline and at Day 90.

In the event that CSRT is missing for Day 90, the analysis will follow an LOCF (Last Observation Carried Forward) approach for the FAS.

The primary analysis will be performed on the FAS.

For sensitivity purposes, the primary analysis will be repeated using the PPS.

2.2.2 Secondary objectives

2.2.2.1 Variables

Secondary variables are:

From OCT

- Change from baseline to visits up to Day 180 in
 - Subfoveal Retinal Thickness (SRT) (*GRADE*: SUBFOVTK),
 - Central Subfield Retinal Thickness (CSRT) (*GRADE*: CSTTHK),
 - Central Subfield Retinal Volume (CSRV) (*GRADE*: CSRVVOL).
- Presence or absence of qualitative OCT parameters:
 - Intraretinal fluid (*GRADE*: RETFL),
 - Intraretinal fluid of cystoid origin (*GRADE*: RETIRC)
 - Subretinal fluid (SF) (*GRADE*: RETFLSF)
 - Intraretinal/subretinal fluid within the central subfield (diameter 1000 microns) (*GRADE*: RETSF)
 - Pigment epithelial detachments (PEDs) (*GRADE*: PEDDET),

- Dry retina. Dry retina is defined as eye without intraretinal fluid (RETFL from derived.grade) AND eye without subretinal fluid (RETFLSF from derived.grade) AND eye without intraretinal cysts (RETIRC from derived.grade)
- Change from baseline to visits up to Day 180 in PED height (*GRADE*: PEDHEIGHT) and diameter (*GRADE*: PEDDIAM) and IRC height (*GRADE*: IRCHEIGHT).
- Frequency of qualitative change OCT parameters:
 - Change from previous visit, each visit up to Day 180 in intraretinal fluid (*GRADE*: INTRAFL)
 - Change from previous visit, each visit up to Day 180 in subretinal fluid (SF) (*GRADE*: SUBRETFL)
 - Change from previous visit, each visit up to Day 180 in intraretinal/subretinal fluid within the central subfield (*GRADE*: SUBCENT)
 - Change from previous visit, each visit up to Day 180 in the pigment epithelium detachment (PED). (*GRADE*: CHAGPED)

or **From visual acuity (for study eye and fellow eye)**

- Change in BCVA from baseline to visits up to Day 180.
- Change in BCVA from Day 90 to Day 180.
- Proportions of patients with change from baseline in ETDRS letters for the following categories ≤ -15 , > -15 to < 0 , ≤ 0 to < 5 , ≥ 5 to < 10 , ≥ 10 to < 15 and ≥ 15 ETDRS letters from baseline at visits up to Day 180.

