**Table 6-1 Assessment schedule (Eligibility criteria, demographics & baseline characteristics, imaging procedures)**

	Screening V1	Baseline V2	V3	V4	PEV V5	V6	V7	EOS or EWV V8	UNSCHED V
Days relative to Day 1 (permitted time window)	Primary treatment failure≤40 days Suboptimal treatment response≤70 days prior to Baseline visit	1	30±7	60±7	90±7	120±7	150±7	180±7	
Informed consent	X								
Review of inclusion/exclusion criteria	X	X							
Diagnosis	X								
Demography	X								
Medical History	X	X							
Prior/concomitant meds	X	X	X	X	X	X	X	X	X
Serum pregnancy test	X								
BCVA score (ETDRS)	X*	X*	X	X	X*	X	X	X*	X*
Historical retinal images collected	X								
Ophthalmic examination	X	X	X	X	X	X	X	X	
OCT (retina and choroid)	X	X	X	X	X	X	X	X	
Color fundus photography	X							X	
Fluorescein angiography	X							X	
Fundus autofluorescence	X							X	
Indocyanine green angiography	X								
PEV: Primary Endpoint Visit. EOS: End of Study visit also incorporates the Early Withdrawal Visit (EWV). UNSCHED V: Unscheduled visit * Assessment to be performed also on fellow-eye; where ranibizumab treatment is initiated in the fellow-eye BCVA is to be repeated and recorded in the eCRF prior to injection.									

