### **6.5.2 Fellow eye**

In order to characterize the patient and collect safety data, the assessment of BCVA will be performed in the fellow-eye (treated or not treated with ranibizumab) at Screening, Baseline (Day 1), Day 90 and Day 180. AEs and SAEs for the fellow eye will be recorded at every visit. Data will be recorded in the eCRF.

At the time when treatment of the fellow eye occurs, the BCVA assessment should be repeated prior to injection of ranibizumab and the data recorded in the eCRF.

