2.1 Patients and treatments

2.1.1 Analysis sets

Assignment of patients to analysis sets will be agreed between the study statistician and the Sponsor prior to database lock, once all study data are available and verified. All efficacy analyses will be performed on the study eye. For visual acuity tests, the results for the fellow eye (non-study eye) will also be summarized for reference.

Full Analysis Set (FAS): The FAS consists of all patients who received at least one application of study treatment in the study eye, have baseline and have at least one post-baseline assessment for CSRT. Following the intent-to-treat principle, patients will be analyzed according to the treatment assigned. No data will be excluded from the FAS analyses because of protocol deviations.

Per Protocol Set (PPS): The PPS consists of all patients in the FAS who followed the assigned treatment and completed the study without clinically significant protocol deviations.

Safety Set (SAF): The SAF consists of all patients who received at least one application of study treatment in the study eye and had at least one post-baseline safety assessment.

All efficacy evaluations will be carried out on the Full Analysis Set and all safety evaluations will be carried out on the Safety Set. For sensitivity purposes, the primary analysis will be repeated using the Per Protocol Set. Any major discrepancies in the results across analyses will be investigated as necessary.

In addition, 2 subgroups of patients are defined:

- Group 1. Primary treatment failure (PTF)
- Group 2. Suboptimal treatment response (STR)

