2.2.2.2 Descriptive analyses

The analysis of the secondary efficacy objectives will be performed on the FAS.

No replacement of missing data will be done.

[figure not shown]
Data from visual acuity will be summarized for study eye and fellow eye separately.

[figure not shown]
Continuous secondary variables will be summarized presenting the absolute values and changes from baseline by visit, and will also be plotted over time.

[figure not shown]
Waterfall plot for change in number of letters for BCVA will be presented.

[figure not shown]
Qualitative secondary variables will be summarized presenting the number and percentage of patients for each modality by visit, and will also be presented graphically over time using bar charts.

All secondary variables details, including derived variables, will be listed.

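### Fellow-eye BCVA is summarised and plotted by visit up to Day 180, but after baseline it is scheduled only at Day 90 and Day 180, so the other four points would rest on treatment-selected eyes

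*SAP*

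**What the plan says.** **SAP.** Section 2.2.2.1 heads the visual-acuity variables "From visual acuity (for study eye and fellow eye". The first is "Change in BCVA from baseline to visits up to Day 180". The others are the change from Day 90 to Day 180 and the proportions in letter-change categories at visits up to Day 180. Section 2.2.2.2 adds "Data from visual acuity will be summarized for study eye and fellow eye separately", then "Continuous secondary variables will be summarized presenting the absolute values and changes from baseline by visit, and will also be plotted over time". Categorical variables get counts, percentages and bar charts by visit. On missing data it says "No replacement of missing data will be done". Section 2.1.1 gives the status of the fellow-eye output: "For visual acuity tests, the results for the fellow eye (non-study eye) will also be summarized for reference". Section 2.5 repeats all the section 2.2.2 tables and listings at the interim analysis of the first 50 patients, whose results are to be submitted for publication.

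**Protocol.** Section 6.5.2 places fellow-eye BCVA "at Screening, Baseline (Day 1), Day 90 and Day 180". Table 6-1 agrees. The asterisk that adds the fellow eye stands at V1, V2, V5, V8 and the unscheduled visit, while V3, V4, V6 and V7 carry a plain X. The table footnote adds a trigger outside the schedule: "where ranibizumab treatment is initiated in the fellow-eye BCVA is to be repeated and recorded in the eCRF prior to injection". Section 5.5.4.3 describes the fellow eyes concerned, which are those the investigator judges to have visual impairment from nAMD that needs treatment. It allows bilateral injection at any scheduled visit from Day 30 to Day 150.

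**The concern.** The SAP sets the same by-visit output for both eyes, but the two eyes are not measured on the same schedule. The study eye is tested at every scheduled visit. The fellow eye is tested in all attending patients at only two post-baseline visits, and between them only if it is being treated.

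This is more than sparse data, because whether a value exists depends on the condition of the eye. With no replacement of missing values, a by-visit mean or category percentage at Days 30, 60, 120 and 150 describes eyes selected by a clinical decision taken after baseline. Joining those points to Days 90 and 180 gives a line whose membership switches between treated eyes and all eyes. It could move with no change in any patient, and it could not serve as the reference that SAP 2.1.1 intends. The same problem would carry into the interim results sent for publication.

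**Working it through.** The plan states no figure to reproduce here. The check sets the SAP's visits against the protocol's schedule.

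**Step 1: who has a fellow-eye value at each post-baseline visit (Table 6-1; protocol 6.5.2 and 5.5.4.3)**

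| Visit | Day | Fellow-eye BCVA scheduled | Who supplies a value |
|---|---|---|---|
| V3 | 30 | No | Fellow eyes being treated |
| V4 | 60 | No | Fellow eyes being treated |
| V5 | 90 | Yes | All attending patients |
| V6 | 120 | No | Fellow eyes being treated |
| V7 | 150 | No | Fellow eyes being treated |
| V8 | 180 | Yes | All attending patients |

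Scheduled post-baseline visits without fellow-eye BCVA: 6 − 2 = 4. Up to Day 90, the horizon of the interim analysis: 3 − 1 = 2 of 3.

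**Step 2: other sources of values.** Unscheduled visits record BCVA in both eyes (protocol section 6 and Table 6-1). The visible SAP text has no rule that assigns such values to a nominal visit, so they do not fill Days 30, 60, 120 or 150. Protocol 5.5.4.3 prefers fellow-eye injection on the day of a scheduled visit, so treatment-triggered values will tend to fall on the days being plotted.

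**Step 3: number of eyes.** Exclusion criterion 12 (protocol 4.2) removes patients whose two eyes both need injections at entry. Treated fellow eyes at any one visit are therefore probably few, but the documents give no rate.

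**Step 4: what could happen to the mean.** Let f be the share of fellow eyes treated at an off-schedule visit, m1 their mean change from baseline, and m0 the mean change in the rest. The plotted mean is m1. The mean over all eyes would be f·m1 + (1 − f)·m0. The displacement is

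m1 − [f·m1 + (1 − f)·m0] = (1 − f)(m1 − m0).

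The documents give none of f, m1 or m0. The values below are assumptions that show the mechanism only.

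- f from 0.03 to 0.15. With the protocol's 124 patients this is 124 × 0.03 = 3.7 to 124 × 0.15 = 18.6 eyes. The displacement itself does not depend on the number of patients.
- The factor (1 − f) then runs from 0.97 to 0.85, so nearly all of any difference between treated and other eyes appears in the plotted point.
- If m1 − m0 = −5 letters, the displacement is −4.85 to −4.25.
- If m1 − m0 = +5 letters, it is +4.85 to +4.25.
- If m1 − m0 = 0, it is 0.

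**Step 5: can the sign be fixed?** No. Treatment for visual impairment suggests a loss when treatment starts. But criterion 12 also admits fellow eyes with quiescent CNV that were treated earlier, and section 5.5.4.3 allows repeat injections. The protocol also disagrees with itself on the trigger. Section 5.5.4.3 and Table 6-1 tie the extra BCVA to the start of fellow-eye treatment, while section 6.5.2 ties it to treatment taking place. Under the second wording, some values come from eyes already responding to an earlier injection.

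**The case against.** The strongest reply is that the SAP never says every visit. Its opening section ties assessments to Tables 6-1 and 6-2, so a programmer could take by visit to mean visits at which that eye is scheduled. No table shells are visible, and the final outputs may already be limited in this way. The fellow-eye results are descriptive and for reference, no comparison between eyes is planned, and SAP section 2 requires n in continuous summaries, so a collapse in numbers would show in the table.

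Much of this stands, and it keeps the point modest. But the schedule sentence governs when assessments are made, not which visits are reported. Nothing visible restricts the fellow-eye output, and the SAP does not require n on the plots. The general statements that assessments or parameters cover both eyes (protocol 6.5 and 9.1) give no BCVA schedule and do not displace Table 6-1 and section 6.5.2. They might lead some sites to test untreated fellow eyes off schedule, so the share of treated eyes at those visits is not known exactly.

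A reader might infer more than the documents support:

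- *That the curve will show false falls between scheduled visits and recoveries at Days 90 and 180.* This needs a treatment rate and a letter change that the documents do not give, and the sign is open.
- *That the study eye will look better by comparison.* The SAP summarises the eyes separately and plans no such comparison.
- *That off-schedule values come only from eyes with newly developed nAMD.* Criterion 12 and the repeat-injection provision say otherwise.

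**Conclusion.** The mismatch holds. As written, SAP 2.2.2.1 and 2.2.2.2 call for fellow-eye BCVA output at visits up to Day 180, and at 4 of 6 scheduled post-baseline visits (2 of 3 up to Day 90) the protocol provides values only from eyes being treated. Those points would describe a treatment-selected and probably small subset, and the curve could move through changing membership alone. This rests on sites following the schedule and on the SAP being applied without a restriction that is not visible.

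The direction and size of any distortion cannot be derived. The consequence is limited to a descriptive reference output, including its interim version. The primary endpoint (CSRT at Day 90) and study-eye BCVA are unaffected. The change is still worth making because it removes a known source of selection at almost no cost.

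**What to change.** - In SAP 2.2.2.1 and 2.2.2.2, state that fellow-eye BCVA by-visit summaries, letter-change categories and plots cover Baseline, Day 90 and Day 180 only, plus the change from Day 90 to Day 180. Section 2.2.2.2 names no eye or visit for the waterfall plot; if one is drawn for the fellow eye, apply the same limit.
- In SAP 2.5, limit the interim fellow-eye BCVA output to Baseline and Day 90.
- Put fellow-eye BCVA from other scheduled visits and from unscheduled visits in listings only.
- Reconcile protocol 5.5.4.3 and Table 6-1 with section 6.5.2 on whether the extra fellow-eye BCVA is due when treatment starts or whenever it is given, so that the listed values can be interpreted.

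Do not split the summaries into treated and untreated fellow eyes. That groups eyes on an event after baseline and is not needed to repair the mismatch.

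The cost is SAP wording, one protocol clarification and fewer descriptive columns. No new data are needed, and the off-schedule values remain available in the listings.
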